5.3 Venetoclax Administration

-If a dose is missed or vomited, the next dose should not be increased to account for missing a dose. The subject should take the next regular dose at the regularly scheduled time.

-Day 1 of each cycle will be counted from the start of the azacitidine infusion. Treatment may be prolonged beyond the

Nivolumab and azacytidine planned 28 days of each cycle if the start of the next course of azacitidine is delayed. However, if there are adverse events that mandate treatment interruption or it is considered in the best interest of the patient for safety reasons to interrupt nivolumab and/or venetoclax therapy, nivolumab and/or venetoclax administration can be transiently discontinued and re-started as per guidelines in section 6.0.

5.3.0 Dose Adjustments

Toxicity Directly Attributable to Study Drugs

Patients experiencing unacceptable toxicity directly attributable to the study drugs should temporarily stop treatment according to the guidelines in the dose adjustment schema.

5.3.1 Nivolumab, Ipilimumab, Venetoclax and 5-azacytidine dose adjustments for hematological drug- related adverse events (AE):

Dose reduction/interruption/discontinuation decisions should be based on the CTCAE version 4.0 (Appendix C) of the toxicity and the guidelines provided below.

- Patients with acute leukemia's usually present with abnormal peripheral blood counts at the time therapy is started and myelosuppression is an expected event during the course of therapy for acute leukemia's. Thus, no dose adjustments or treatment interruptions for myelosuppression

will be planned for the first 4 cycles and/or in the presence of residual leukemia. After that, treatment interruptions and dose adjustments may be considered according to the following guidelines only when there is no evidence of active leukemia (e.g., only if <5% blasts in the bone marrow by morphology or flow-cytometry or cytopenias not considered to be related to leukemia).

- Patients with a response (no marrow evidence of leukemia) and pre-cycle counts of neutrophils $>1 \times 10^9/L$ and platelets $>50 \times 10^9/L$ who have sustained low counts of neutrophils $<0.5 \times 10^9/L$ or a platelet count $<20 \times 10^9/L$ for more than 2 consecutive weeks in the current cycle, may have the treatment with 5-azacytidine and/or venetoclax interrupted at the discretion of the treating physician after discussing with the PI until neutrophils recover to $\geq 1 \times 10^9/L$ and platelets to $\geq 50 \times 10^9/L$. Nivolumab and ipilimumab have not been associated with neutropenia and/or thrombocytopenia in prior studies and should generally not be interrupted or discontinued for myelosuppression.

- If there are persistent peripheral blood blasts, or the bone marrow shows >5% blasts or evidence of leukemia by flow cytometry, treatment may be continued regardless of neutrophil and platelet count with supportive care as needed. Dose-interruptions of 5- azacytidine and/or venetoclax in these patients should be considered on an individual case and discussed with the PI.
- Patients with a response (no marrow evidence of leukemia) and pre-cycle counts of neutrophils $<1 \times 10^9/L$ and platelets $<50 \times 10^9/L$ may be continued regardless of neutrophil and platelet count with supportive care as needed. Dose-interruptions of 5- azacytidine and/or venetoclax in these patients should be considered on an individual case and discussed with the PI.
- Investigators should, whenever possible, determine which medication is causing the toxicity and interrupt or dose reduce 5-azacytidine and/or venetoclax and/or interrupt nivolumab and/or ipilimumab or both, as applicable. No dose reductions are permitted for nivolumab and ipilimumab once the RP2D is established. Nivolumab and ipilimumab have not been associated with neutropenia and/or thrombocytopenia in prior studies and should generally not be interrupted or discontinued for myelosuppression.

5.3.2 Nivolumab, Ipilimumab, Venetoclax and 5-azacytidine dose adjustments for non-hematologic drug- related AEs

Investigators should, whenever possible, determine which medication is causing the toxicity and interrupt or dose reduce 5-azacytidine and/or venetoclax or interrupt nivolumab or ipilimumab or both, as applicable. No dose reductions (only interruptions) are permitted for nivolumab and ipilimumab.

Dose reductions of azacitidine will be as follows: Baseline dose level: 75 mg/m² x 7 days, dose level -1 of azacitidine: 50 mg/m² x 7 days, dose level -2: 37.5 mg/m² x 7 days, dose level -3: 25 mg/m² x 7 days. Further reductions or modifications to schedule beyond what is shown above or alternative reductions (e.g. 75mg/m² x 5 days) may be allowed if deemed in the patient's best interest by the treating physician.

Dose reductions of venetoclax will be as follows: Baseline dose level of venetoclax: 400mg, dose level -1 of venetoclax: 200mg, dose level -2: 100mg, dose level -3, 50mg. Alternatively, the duration of venetoclax administration can be decreased (e.g. decrease from 21-days per cycle to 14-day per cycle to 10 days per cycle) rather than the dose being reduced.

Table 6A Arm 1: Dose adjustments for non-hematologic drug-related AEs, clinically significant in the opinion of the investigator

| Grade | Occurrence | Dose modification |
|---|--|---|
| 1 or 2 | Any time | No dose reduction |
| 3 or 4 (Persistent grade 2: Consider similar dose adjustments if persistent and not responding to optimal management in the opinion of PI and treating physician) | 1st and 2nd time | Hold nivolumab and 5-azacytidine. Resume nivolumab and 5-azacytidine at prior dose if recovery to ≤ Grade 1 occurs within 14 days. If toxicity persists for 15-28 days, hold therapy and resume Nivolumab at prior dose and 5-azacytidine at prior dose if recovery to ≤ Grade 1 OR resume nivolumab at prior dose and 5-azacytidine at ONE dose level below current dose if recovery to ≤ Grade 2. Dose re-escalation to prior dose of 5-azacytidine is permitted in accordance with the dose-escalation guidelines in section 5.3.6. |
| | 3 rd and 4 th time | Hold nivolumab and 5-azacytidine. Follow until toxicity ≤ Grade 2. Resume nivolumab at prior dose and 5-azacytidine at ONE dose level below current dose. Dose re-escalation of 5-azacytidine to prior dose is permitted in accordance with the dose-escalation guidelines in section 5.3.6.. |
| | 5th time | Take patient off the study. |

Table 6B Arm 2: Dose adjustments for non-hematologic drug-related AEs, clinically significant in the opinion of the investigator

| Grade | Occurrence | Dose modification |
|---|--|---|
| 1 or 2 | Any time | No dose reduction |
| 3 or 4 (Persistent grade 2: Consider similar dose adjustments if persistent and not responding to optimal management in the opinion of PI and treating physician) | 1st and 2nd time | Hold nivolumab, ipilimumab and 5-azacytidine. Resume nivolumab and/or ipilimumab and 5-azacytidine at prior dose if recovery to ≤ Grade 1 occurs within 14 days. If toxicity persists for 15-28 days, hold therapy and resume nivolumab and/or ipilimumab at prior dose and 5-azacytidine at prior dose if recovery to ≤ Grade 1 OR resume nivolumab and/or ipilimumab at prior dose and 5-azacytidine at ONE dose level below current dose if recovery to ≤ Grade 2. Dose re-escalation to prior dose of 5-azacytidine is permitted in accordance with the dose-escalation guidelines in section 5.3.6. |
| | 3 rd and 4 th time | Hold nivolumab and ipilimumab and 5-azacytidine. Follow until toxicity ≤ Grade 2. Resume nivolumab and ipilimumab at prior dose and 5-azacytidine at TWO dose level below current dose. Dose re-escalation of 5-azacytidine to prior dose is permitted in accordance with the dose-escalation guidelines in section 5.3.6.. |

| | |
|----------|-----------------------------|
| 5th time | Take patient off the study. |
|----------|-----------------------------|

Table 6C Arm 3: Dose adjustments for non-hematologic drug-related AEs, clinically significant in the opinion of the investigator

| Grade | Occurrence | Dose modification |
|---|----------------------|---|
| 1 or 2 | Any time | No dose reduction |
| 3 or 4 (Persistent grade 2: Consider similar dose adjustments if persistent and not responding to optimal management in the opinion of PI and treating physician) | 1st and 2nd time | 
 -Hold most likely offending agent. -Resume nivolumab and/or venetoclax and 5-azacytidine at prior dose if recovery to \leq Grade 1 occurs within 14 days. -If toxicity persists for 15-28 days, hold therapy and resume nivolumab and/or venetoclax at prior dose and 5-azacytidine at prior dose if recovery to \leq Grade 1 OR resume nivolumab at prior dose and 5-azacytidine and venetoclax at ONE dose level below current dose if recovery to \leq Grade 2. -Dose re-escalation to prior dose of 5-azacytidine is permitted in accordance with the dose-escalation guidelines in section 5.3.6.. |
| | 3 rd time | 
 -Hold most likely offending agent. -Follow until toxicity \leq Grade 2. -Resume nivolumab at prior dose and 5-azacytidine and venetoclax at TWO dose level below current dose. -Dose re-escalation of 5-azacytidine to prior dose is permitted in accordance with the dose-escalation guidelines in section 5.3.6.. |
| | 4th time | Take patient off the study. |

5.3.3 Nivolumab or Ipilimumab or both dose delay/interruption for immune-oncology drug-related AEs, clinically significant in the opinion of the investigator

Nivolumab (Arm 1 or 3) or nivolumab+ipilimumab (Arm 2) administration should be delayed for the following drug-related AEs, clinically significant in the opinion of the investigator:

- Any Grade ≥ 2 non -skin AE, except that
 - Grade 2 fatigue or laboratory abnormalities do not require delay, however
 - ◆ Patients with ALT or AST > 3 and up to 5 x ULN or total bilirubin greater > 1.5 and up to 3 x ULN or creatinine > 1.5 and up to 6

Nivolumab and azacytidine

x ULN (or greater than 1.5 times baseline) should have nivolumab (Arm 1 or 3) or nivolumab+ipilimumab (Arm 2) treatment withheld.

- Any Grade 3 skin AE, or Grade 3 laboratory abnormality, with the following exceptions:
 - Grade 3 lymphopenia or leukopenia does not require dose delay.
 - However, patients with ALT or AST >5 x ULN or total bilirubin greater >3 x ULN or creatinine >6 x ULN should be discontinued from nivolumab treatment (Arm 1 or 3) or nivolumab and ipilimumab treatment (Arm 2).
- Any AE, laboratory abnormality, or intercurrent illness, which in the judgment of the investigator, warrants delaying the dose of study medication.
- Nivolumab and ipilimumab dose reductions are not permitted in this study (only dose delays when indicated).

Subjects may resume treatment with nivolumab (Arm 1 and 3) or nivolumab and ipilimumab (Arm 2) with study drug when the drug-related AE(s) resolve to Grade ≤ 1 or baseline value, with the following exceptions:

- Subjects may resume treatment in the presence of Grade 2 fatigue
- Subjects who have not experienced a Grade 3 drug-related skin AE may resume treatment in the presence of Grade 2 skin toxicity
- Drug-related pulmonary toxicity, diarrhea, or colitis, must have resolved to baseline before treatment is resumed
- Drug-related endocrinopathies adequately controlled with only physiologic hormone replacement may resume treatment

If the criteria to resume treatment are met, the subject should restart treatment at the next scheduled timepoint per protocol. However, if the treatment is delayed past the next scheduled timepoint per protocol, the next scheduled timepoint will be delayed until dosing resumes. Patients who receive combination therapy in whom continuation of 5-azacytidine and/or venetoclax is considered to be inadequate, or inappropriate (e.g., because of pancytopenia) can discontinue 5-azacytidine and/or venetoclax and continue with nivolumab only.

If treatment is delayed > 8 weeks, the subject must be permanently discontinued from study therapy, except as specified in discontinuation section. Delays in start of subsequent cycles greater than 8 weeks will be acceptable only for patients who are deriving clinical benefit and after discussion with the principal investigator of potential risk/benefit ratio.

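### After a prolonged or repeated Grade 3-4 event, Tables 6A-6C let nivolumab or ipilimumab restart at Grade 2, section 5.3.3 requires Grade 1 or baseline for immune-oncology events, and no visible text says which governs

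*Combined protocol and SAP*

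**What the plan says.** Section 5.3.2 sets dose adjustments for non-hematologic drug-related events and names all four drugs. It asks investigators to identify the causative drug where possible and then to "interrupt or dose reduce 5-azacytidine and/or venetoclax or interrupt nivolumab or ipilimumab or both, as applicable". Its tables carry these restart rules for Grade 3-4 events:

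- **Recovery within 14 days, first or second event (all arms):** restart at the prior dose at Grade 1 or lower.
- **Toxicity lasting 15-28 days, first or second event:** a second option is added. Table 6A (Arm 1) reads "resume nivolumab at prior dose and 5-azacytidine at ONE dose level below current dose if recovery to ≤ Grade 2". Table 6B gives the same option for nivolumab and/or ipilimumab. Table 6C (Arm 3) reads "OR resume nivolumab at prior dose and 5-azacytidine and venetoclax at ONE dose level below current dose if recovery to" Grade 2 or lower.
- **Third or fourth event (third only in Table 6C):** Table 6B reads "Hold nivolumab and ipilimumab and 5-azacytidine. Follow until toxicity ≤ Grade 2. Resume nivolumab and ipilimumab at prior dose". Tables 6A and 6C use the same Grade 2 threshold for nivolumab.

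Section 5.3.3 is headed "Nivolumab or Ipilimumab or both dose delay/interruption for immune-oncology drug-related AEs". It allows these drugs to restart "when the drug-related AE(s) resolve to Grade ≤ 1 or baseline value, with the following exceptions". The exceptions that tolerate more than Grade 1 are Grade 2 fatigue, hormone-controlled endocrinopathy, and one for skin: "Subjects who have not experienced a Grade 3 drug-related skin AE may resume treatment in the presence of Grade 2 skin toxicity". Pulmonary toxicity, diarrhea and colitis must return to baseline.

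Section 5.3.4 permanently discontinues the checkpoint inhibitor for most Grade 4 events, for non-skin Grade 3 events lasting more than 7 days, and for a list of Grade 3 events (pneumonitis and colitis among them) of any duration.

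**The concern.** The tables and section 5.3.3 both give explicit restart thresholds for the same drugs, and their scopes overlap: an immune-oncology rash is also a non-hematologic drug-related event. The tables do not exclude immune-oncology events or point to section 5.3.3, and section 5.3.3 does not say that it overrides the tables.

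The threshold carries weight because nivolumab and ipilimumab may not be dose-reduced (sections 5.2.1, 5.3.2 and 5.3.3). Holding, restarting and stopping are the only dosing controls over their toxicity. A physician who follows the tables may re-dose a patient whom section 5.3.3 would keep on hold. Section 9.3 also lists noncompliance with interruption or delay rules as a class of violation or deviation, so compliance with one section could be recorded as a departure from the other.

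**Working it through.** No statistical figure is at issue. The check is to take one patient through each rule and then see how far the conflict extends.

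**Case 1: Grade 3 rash attributed to the checkpoint inhibitor, first occurrence, still Grade 2 on day 20.**

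| Rule | Relevant condition | Instruction |
|---|---|---|
| Tables 6A-6C | Day 20 lies within 15-28 days; recovery to Grade 2 | Nivolumab (6B: and/or ipilimumab) may restart at prior dose; azacitidine, and venetoclax in Arm 3, one level lower |
| 5.3.3 | The Grade 2 skin exception excludes anyone with a previous Grade 3 skin event | Do not restart until Grade 1 or baseline |
| 5.3.4 | The 7-day Grade 3 rule is limited to non-skin events | No discontinuation, so the question stays open |

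The same patient gets opposite instructions.

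**Case 2: Grade 3 non-skin clinical event.** If it is off the any-duration list and at Grade 3 for 7 days or less, section 5.3.4 does not discontinue it. If it then settles at Grade 2 and is still there at days 15-28, or if it is a third event, the tables allow a restart and section 5.3.3 does not. Fatigue and controlled endocrinopathy are excepted in section 5.3.3 and so do not conflict.

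**Where there is no conflict, or none is claimed.**
- First or second events that recover within 14 days: both rules require Grade 1 or lower.
- Events that section 5.3.4 discontinues.
- Persistent Grade 2 events: the tables only say "Consider similar dose adjustments if persistent and not responding to optimal management in the opinion of PI and treating physician", which is discretionary.
- Grade 2 laboratory values outside the ALT/AST, bilirubin and creatinine limits: section 5.3.3 does not delay treatment for these, so they are not a clean clash with the tables.

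**Possible tie-breakers.** Section 5.3.5 refers to the Appendix G algorithms but calls them guidance. Item 5.3.7.4, under section 5.3.10, allows approved modifications other than those already listed. Neither ranks the tables against section 5.3.3.

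**How often.** The documents give only the pool from which conflict cases could come.
- Arm 2 (section 2.3 D): 6 of 24 evaluable patients had Grade 3/4 immune toxicity, including rash, pneumonitis and colitis. Assuming one event per patient and at least one of each type, Grade 3/4 rash occurred in 1 to 6 − 1 − 1 = 4 patients, or 1/24 = 4.2% to 4/24 = 16.7%. This is not a conflict rate: Grade 4 rash is discontinued, and only rash remaining at Grade 2 at days 15-28, or a third or later event, would qualify.
- Arm 1 (section 2.3 C): 1 rash, of unstated grade, among 8 + 2 + 2 + 1 = 13 immune episodes in 51 patients (1/51 = 2.0%). All 12 surviving cases responded rapidly to steroids. Their grade at re-dosing is not given.
- Repeat events: section 2.6 (rationale) reports recurrence in 1 of 15 patients continued on nivolumab (6.7%), so third occurrences should be rare. Its count of 15 differs from the 13 in section 2.3 C.

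**The case against.** The best defense is structural. Section 5.3.2 is the general rule, while sections 5.3.3 and 5.3.4 are specific to immune-oncology drugs and events. Investigators are told to attribute the event, and item 5.3.7.4 gives autoimmune thyroiditis and hepatitis as examples likely to be due to the checkpoint inhibitors. The tables' Grade 2 option also lowers azacitidine (and venetoclax in Arm 3), which suits an event those drugs helped to cause better than a purely immune rash. A sensible reader would probably let section 5.3.3 prevail.

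That is a fair account of the likely intent, but it remains an inference. Tables 6A and 6B hold and restart the checkpoint inhibitors whatever the attribution. Table 6C holds the most likely offending agent, so when that is nivolumab the Grade 2 threshold applies to it directly.

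Appendix G also limits the claim. Sections 5.3.5 and 5.5 send investigators to algorithms that cover skin, and their content is not in the available text. The statement that nothing ranks the two rules is therefore confined to what can be read.

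A reader might infer that the protocol generally permits re-dosing of unresolved immune toxicity, or that patients were re-dosed against section 5.3.3. The documents support neither. The looser threshold is confined to prolonged or repeated events, section 5.3.4 removes most severe ones, and no conflict case is reported.

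**Conclusion.** The inconsistency is real and minor. It is firm for a Grade 3 rash that improves only to Grade 2 and is still there at days 15-28, or at a third or fourth event (third in Arm 3). It extends more narrowly to Grade 3 non-skin clinical events that section 5.3.4 does not discontinue and that settle at Grade 2. This rests on the event being attributed at least partly to nivolumab or ipilimumab, and on Appendix G not settling the matter.

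Frequency cannot be estimated, because neither the duration at Grade 2 nor the grade at re-dosing is reported. It is probably low and may be zero; the rash counts above describe a pool, not a rate of conflict.

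A reader might also suspect an effect on the efficacy or monitoring results. There is none: neither the ORR definitions nor the stopping boundaries use the restart threshold, and the toxicity boundaries count patients with a drug-related Grade 3/4 event, so a patient with Grade 3 rash is already counted. Section 11.3 lists both Arm 1 cohorts as closed to accrual, so the practical interest lies in Tables 6B and 6C.

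**What to change.** Add the following to section 5.3.2, with a cross-reference in the Grade 3/4 rows of Tables 6A-6C:

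> For any AE attributed to nivolumab or ipilimumab, alone or jointly with another study drug, Sections 5.3.3 and 5.3.4 govern delay, resumption and discontinuation of nivolumab and ipilimumab; Tables 6A-6C then govern only azacitidine and venetoclax. The Grade ≤2 resumption threshold in the tables applies to nivolumab or ipilimumab only when the AE is attributed solely to azacitidine and/or venetoclax.

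Naming joint attribution matters in a combination regimen: without it, an event ascribed to both azacitidine and nivolumab could fall under either rule. If re-dosing at Grade 2 after a Grade 3 rash is intended, add it to the section 5.3.3 exceptions instead.

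The drafting cost is two sentences and one cross-reference per table. The clinical cost is longer holds of the checkpoint inhibitor in a few patients, including some with mixed-attribution events, to whom the section 5.3.4 discontinuation criteria would then plainly apply.

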5.3.4 Nivolumab (Arm 1 and 3) or nivolumab+ipilimumab (arm 2) Discontinuation Criteria

Treatment with IO-agent/s should be permanently discontinued for the following:

- Any Grade 2 drug-related uveitis or eye pain or blurred vision that does not respond to topical therapy and does not improve to Grade 1 severity within the re-treatment period OR lasting > 7 days with systemic treatment.

- Any Grade 3 non-skin, drug-related adverse event lasting > 7 days, with the following exceptions for drug-related laboratory abnormalities, uveitis, pneumonitis, bronchospasm, diarrhea, colitis, neurologic adverse event, hypersensitivity reactions, and infusion reactions:
 - Grade 3 drug-related uveitis, pneumonitis, bronchospasm, diarrhea, colitis, neurologic adverse event, hypersensitivity reaction, or infusion reaction of any duration requires discontinuation
 - Grade 3 drug-related laboratory abnormalities do not require treatment discontinuation except those noted below:
 - Any drug-related liver function test (LFT) abnormality that meets the following criteria require discontinuation: ALT or AST >5 x ULN or total bilirubin greater > 3 x ULN or creatinine >6 x ULN
- Any Grade 4 drug-related adverse event or laboratory abnormality, except for the following events which do not require discontinuation:
 - Isolated Grade 4 amylase or lipase abnormalities that are not associated with symptoms or clinical manifestations of pancreatitis and decrease to < Grade 4 within 1 week of onset.
 - Isolated Grade 4 electrolyte imbalances/abnormalities that are not associated with clinical sequelae and are corrected with supplementation/appropriate management within 72 hours of their onset
- Any dosing interruption lasting > 8 weeks with the following exceptions:
 - Dosing interruptions to allow for prolonged steroid tapers to manage drug-related adverse events are allowed. Prior to re-initiating treatment in a subject with a dosing interruption lasting > 8 weeks, the Principal Investigator must be consulted. Tumor/Leukemia assessments should continue as per protocol even if dosing is interrupted.
 - Dosing interruptions > 8 weeks that occur for non-drug-related reasons may be allowed if approved by the Principal Investigator. Prior to re-initiating treatment in a subject with a dosing interruption lasting > 8 weeks, the Principal Investigator must be consulted. Tumor/Leukemia assessments should continue as per protocol even if dosing is interrupted.
 - Delays in start of subsequent cycles greater than 8 weeks will be acceptable only for patients who are deriving clinical benefit and after discussion with the principal investigator of potential risk/benefit ratio.

5.3.5 Detailed management algorithms for immune-oncology drug-related adverse events (including gastrointestinal, renal, pulmonary, hepatic, endocrine, skin and

neurological) are provided in Appendix G. These general guidelines constitute guidance to the Principal Investigator and may be supplemented by discussions with the IND Sponsor in specific cases.

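### For grade 3 or 4 events attributed to nivolumab or ipilimumab, Tables 6A and 6B and two options of Table 6C direct resumption where section 5.3.4 requires permanent discontinuation, and the text does not say which governs

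*Combined protocol and SAP*

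**What the plan says.** Section 5.3.2 of the combined protocol and SAP covers dose adjustment for non-haematologic drug-related events and names nivolumab and ipilimumab in its title. Its three tables put grades 3 and 4 in one row.

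- **Table 6A (Arm 1).** First and second time: hold, then restart nivolumab on recovery to grade 1 or less within 14 days. If toxicity lasts 15 to 28 days, restart at grade 1 or less, or at grade 2 or less "resume nivolumab at prior dose and 5-azacytidine at ONE dose level below current dose". Third and fourth time: restart nivolumab once at grade 2 or less. Off study at the fifth.
- **Table 6B (Arm 2).** The same layout. The late option for the first and second time reads "resume nivolumab and/or ipilimumab at prior dose and 5-azacytidine at ONE dose level below current dose if recovery to" grade 2 or less. The third and fourth time: "Resume nivolumab and ipilimumab at prior dose and 5-azacytidine at TWO dose level below current dose".
- **Table 6C (Arm 3).** Hold whichever drug is thought responsible. Two options name nivolumab outright: recovery to grade 2 or less at 15 to 28 days ("resume nivolumab at prior dose and 5-azacytidine and venetoclax at ONE dose level below current dose") and the third occurrence ("Resume nivolumab at prior dose and 5-azacytidine and venetoclax at TWO dose level below current dose"). The other options say nivolumab and/or venetoclax, so they do not compel nivolumab.

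Section 5.3.3 is headed "Nivolumab or Ipilimumab or both dose delay/interruption for immune-oncology drug-related AEs". It lets IO treatment restart at grade 1 or less or at baseline, with listed exceptions; pulmonary toxicity, diarrhoea and colitis must be back to baseline.

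Section 5.3.4 requires permanent IO discontinuation for "Any Grade 4 drug-related adverse event or laboratory abnormality, except for the following events which do not require discontinuation" (isolated amylase/lipase and isolated electrolyte abnormalities, under conditions). It adds "Grade 3 drug-related uveitis, pneumonitis, bronchospasm, diarrhea, colitis, neurologic adverse event, hypersensitivity reaction, or infusion reaction of any duration requires discontinuation". It also covers other grade 3 non-skin, non-laboratory events lasting more than 7 days, and ALT/AST, bilirubin or creatinine above its limits. Recovery does not reopen treatment.

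**The concern.** For an event attributed to an IO agent, a physician who follows the tables may restart a checkpoint inhibitor that 5.3.4 says must be stopped for good, for example after grade 4 colitis or grade 3 pneumonitis. The decision concerns patient safety, and two operative instructions answer it in opposite ways. Section 9.3 lists noncompliance with discontinuation criteria among the classes of protocol violation or deviation, so the act one section directs could be recorded as a departure under another.

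The point is limited to events attributed to nivolumab or ipilimumab. Where azacitidine or venetoclax alone is the cause, restarting the IO agent is sensible, and sections 5.3.2 and 5.3.10 tell the investigator to act on the responsible drug.

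**Working it through.** The plan gives no figure to reproduce here; the check is a comparison of instructions. Each case below is an IO-attributed event, first occurrence unless stated.

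| Case | Tables | Sections 5.3.3 and 5.3.4 |
|---|---|---|
| Grade 4 colitis, grade 1 by day 14 | 6A restarts nivolumab; 6B restarts at least one IO agent; 6C does not compel | 5.3.4: stop permanently |
| Grade 3 pneumonitis, grade 1 by day 14 | As above | 5.3.4: stop, any duration |
| Unlisted grade 3 non-skin, non-laboratory event, at grade 3 for 10 days, grade 1 by day 14 | As above | 5.3.4: stop, since 10 > 7 |
| The same event, at grade 3 for 5 days | As above | No conflict with 5.3.4, since 5 ≤ 7 |
| Grade 4 colitis, grade 2 at day 20 | 6A, 6B and 6C each offer a restart | 5.3.4: stop; 5.3.3 would also require baseline |
| Third occurrence, event listed in 5.3.4, now grade 2 | 6A and 6C restart nivolumab; 6B restarts both IO agents | 5.3.4: stop |
| Grade 3 skin event, grade 2 at day 20 | 6A, 6B and 6C each offer a restart | 5.3.4 silent; 5.3.3 wants grade 1 or baseline |
| Isolated grade 4 electrolyte abnormality meeting the exception | Restart on recovery | No conflict with 5.3.4 |

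**Is there a precedence rule?** These are the candidates in the available text.

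- Section 5.3.0 sends toxicity attributable to study drugs to the dose adjustment schema for a temporary stop. It does not rank the tables against 5.3.4.
- Section 5.3.3 refers to the discontinuation section only for delays beyond 8 weeks.
- Section 5.3.10 allows modifications other than those listed, with PI or Co-PI approval. A restart under the tables is one of those listed.
- The tables' only cross-reference is to 5.3.6, for re-escalation of azacitidine. In this version 5.3.6 covers CYP3A4 inhibitors.
- Section 5.3.5 points to Appendix G, which is not in the available text. Sections 5.3.5 and 5.5 describe such algorithms as guidance.
- Section 5.3.3 (liver and creatinine limits) and section 6.1.5 (grade 3 or 4 infusion reactions) agree with 5.3.4 on their own events.

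**How common are severe immune events?** Section 2.3 C reports 7 (14%) with grade 3/4 and 6 (12%) with grade 2 immune toxicity in Arm 1. The denominator is inferred: 7/51 = 13.7% and 6/51 = 11.8% match, while 7/70 = 10.0% and 7/35 = 20.0% do not. Section 2.3 D gives 6 patients (25%) among 24 evaluable in Arm 2. The exact 95% limits are the Beta(x, n−x+1) 2.5% quantile and the Beta(x+1, n−x) 97.5% quantile:

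- Arm 1: 7/51 = 13.7% (5.7% to 26.3%)
- Arm 2: 6/24 = 25.0% (9.8% to 46.7%)

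No Arm 3 figure is given. These rates do not measure how often the conflict arises. They include events that 5.3.4 does not stop, such as grade 3 rash. They may also omit infusion reactions, hypersensitivity and events of mixed attribution, which 5.3.4's *drug-related* wording would cover.

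**The case against.** The strongest reply is that the documents already point to the answer. Section 5.3.2 is general, while 5.3.3 and 5.3.4 are specific to the IO agents. On that reading 5.3.4 decides whether an IO agent may continue, and the tables give the dose at which drugs restart; restarting nivolumab at the prior dose fits, because it may not be reduced. Sections 5.3.3 and 6.1.5 side with 5.3.4, and nothing ranks the tables above it. This stands as the natural reading, but it remains inference: the tables name the IO agents, direct their restart and refer to neither section.

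Second, which rule is better is partly a clinical choice. Section 2.3 C reports that all 12 surviving patients with grade 2 to 4 immune toxicity were successfully rechallenged, and the study rationale in section 2.6 reports 15 who could continue nivolumab, with one recurrence. That stands too, and it is why the fix leaves room for stated exceptions. A reader might infer from the conflict that rechallenge has caused harm; the documents do not show that.

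Third, other safeguards exist. Unacceptable toxicity ends treatment in the investigator's judgement (sections 5.4 and 9.1.3), and section 9.3 does not say that following a table is itself a violation. These soften the consequence but do not settle the instruction.

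A reader might also set four restarts under Tables 6A and 6B against none under 5.3.4, or add the 8-14 and 15-28 day windows into 21 days of conflict. Both are theoretical maxima. The first needs 5.3.4 to be passed over at every earlier event, although the tables also count events due to the other drugs. The second mixes two clocks: 5.3.4 times how long grade 3 lasts, and the tables time recovery to grade 1 or 2.

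**Conclusion.** The inconsistency is real and should be corrected. For IO-attributed events that 5.3.4 lists, Tables 6A and 6B direct a restart of at least one IO agent after recovery, and two options of Table 6C direct a restart of nivolumab. A second, smaller mismatch is that some rows accept grade 2 where 5.3.3 requires grade 1 or baseline.

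The number of patients affected is not known from the documents. A reader might treat 7/51 and 6/24 as upper limits; they are not, because they count immune-mediated events only and 5.3.4 is wider in some respects and narrower in others. No effect on overall response rate or on the stopping boundaries is claimed. Both Arm 1 cohorts are closed to accrual (section 11.3), so Table 6A matters only for patients still on treatment; Tables 6B and 6C carry most of the exposure.

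The conclusion assumes that Appendix G and the Investigator Brochures, which could not be checked, contain no binding order of precedence.

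**What to change.** - In 5.3.2, state that for events considered at least possibly related to nivolumab or ipilimumab, sections 5.3.3 and 5.3.4 override Tables 6A to 6C for those agents.
- In 5.3.4, apply the same attribution qualifier to *drug-related*, so that events due only to azacitidine or venetoclax do not end IO treatment.
- Cross-refer to 5.3.3 and 5.3.4 in the grade 3 or 4 rows of all three tables, and check that Appendix G agrees.
- If the sponsor wants rechallenge after some of these events, list them as exceptions in 5.3.4.

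The cost is a short amendment, approved as section 12.0 requires, and a memo to treating physicians at the one centre. The downside is that some patients who could be rechallenged under the tables would stop IO treatment. That number cannot be stated from the documents, and the qualifier will bring in some events of mixed attribution.
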